A Phase III, Open Label, Randomised, Controlled, Multi-Centre Study to Assess the Efficacy and Safety of Savolitinib versus Sunitinib in Patients with MET-Driven, Unresectable and Locally Advanced, or Metastatic Papillary Renal Cell Carcinoma (PRCC)

International Co-ordinating Investigator

[name]

Dana Farber Cancer Institute

[name]

██

Study site(s) and number of patients planned

Approximately 180 patients were planned to be randomised from 5 to 10 countries worldwide in approximately 50 to 75 sites. Recruitment to the study was closed on 22 November 2018. It is now estimated that approximately 50 patients will be randomised from 7 countries.

Study design

This is an open label, randomised, multicentre, global Phase III study designed to evaluate the efficacy of savolitinib compared with sunitinib in patients with MET-driven, unresectable and locally advanced or metastatic papillary renal cell carcinoma (PRCC). Patients can be treatment naïve or previously treated but cannot have previously received sunitinib or a MET inhibitor.

Following signature of the Part 1 Informed Consent Form (ICF), the MET-driven status of the tumour will be determined in archival or, if necessary, fresh tumour by targeted Next Generation Sequencing (NGS) in the sponsor-designated central laboratory. Patients with confirmed MET-driven tumours, based on this testing or based on a pre-existing MET-driven result from the Sponsor-designated laboratory, may then sign the main study (Part 2) ICF. The Part 2 screening assessments must take place within 28 days of signing the ICF for Part 2. Randomisation must take place within 28 days of signing the ICF for Part 2. Patients who fulfil all the eligibility criteria will be randomised in a ratio of 1:1 to receive savolitinib

(600 mg for patients ≥ 50 kg and 400 mg for patients < 50 kg PO QD) or sunitinib (50 mg PO QD). Patients will be stratified based on International Metastatic RCC Database Consortium (IMDC) risk category as well as whether they are treatment naive vs. previously treated with or without a VEGF-TKI. For the purposes of planning, a 6-week period will be called a “cycle”. Treatment with sunitinib will be given daily for 4 weeks on/2 weeks off. Treatment with savolitinib will be given continuously. There is no maximum duration of treatment and patients will continue to receive study medication until one of the discontinuation criteria are met.

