2.3 Safety objectives

Safety objective:	Outcome measure:
To evaluate the safety and tolerability of savolitinib in relation to sunitinib	
 AEs/SAEs adverse events [AEs] as characterised and graded by National Cancer Institute [NCI] Common Terminology Criteria for Adverse Event [CTCAE], collection of clinical chemistry/haematology parameters, liver function tests, echocardiograms and electrocardiograms (ECGs), vital signs including blood pressure (BP) and heart rate

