4. STUDY PLAN AND TIMING OF PROCEDURES

Table 1 Study schedule: Screening, On Study Treatment, Discontinuation and Follow-up

	Part 1 Screening Visit	Part 2 Screening Visit ²	Cycle 1						Cycle 2						Cycle 3 & beyond (every 6 weeks)	EOT ¹⁸	Safety Follow-up ¹⁹	PFS ²²	Overall Survival Follow-Up ²⁰
			D 1	D 8	D 15	D 22	D 29	D 36	D 1	D 8	D 15	D 22	D 29	D 36	D1				
Site Visit	0	1	2	3	4	5	6	7											
Day		-28 to 0	1	8	15	22	29	36	43	50	57	64	71	78	85				
Activity Visit Window			0	± 2d	± 2d	± 2d	± 2d	± 2d	± 2d	± 2d	± 2d	± 2d	± 2d	± 2d	± 7d				
Part 1 Screening Informed Consent Form ¹	X																		
Demography, medical/surgical history ³	X																		
Cancer therapy ⁴	X															X	X	X	X
FFPE tumour sample for MET-driven status ⁶	X																		
██████████ ██████████ ██████████ ██████████	X																		
Main Study (Part 2) Informed Consent Form ¹		X																	
Physical examination		X	X	X	X	X	X	X	X	X	X	X	X	X	X	X*	X ²⁷		
Body weight ²⁵		X	X					X						X					
Vital signs ⁵		X	X	X	X	X	X	X	X	X	X	X	X	X	X	X*	X ²⁷		

Table 1 Study schedule: Screening, On Study Treatment, Discontinuation and Follow-up

	Part 1 Screening Visit	Part 2 Screening Visit ²	Cycle 1						Cycle 2						Cycle 3 & beyond (every 6 weeks)	EOT ¹⁸	Safety Follow- up ¹⁹	PFS ²³	Overall Survival Follow- Up ²⁰
			D 1	D 8	D 15	D 22	D 29	D 36	D 1	D 8	D 15	D 22	D 29	D 36	D1				
Site Visit	0	1	2	3	4	5	6	7											
Day		-28 to 0	1	8	15	22	29	36	43	50	57	64	71	78	85				
Activity Visit Window			0	± 2d	± 2d	± 2d	± 2d	± 2d	± 2d	± 2d	± 2d	± 2d	± 2d	± 2d	± 7d				
Tumour Assessment ¹⁶		X						X							X			X (by institutional call)	
Karnofsky Performance Status		X	X					X							X	X*			
Smoking Status (Y/N) ²⁴		X																	
Haematology		X	X	X	X	X	X	X	X	X					X	X*	X ²⁷		
Clinical Chemistries ²⁹		X	X	X	X	X	X	X	X	X					X	X*	X ²⁷		
Corrected calcium ³¹		X																	
Liver function tests ²¹		X	X	X	X	X	X	X	X	X					X	X*	X ²⁷		
Hepatitis serology ³⁰		X																	
Coagulation ⁷		X ⁷																	
Urinalysis ⁸		X		X	X	X	X	X	X	X					X		X ²⁷		

Table 1 Study schedule: Screening, On Study Treatment, Discontinuation and Follow-up

	Part 1 Screening Visit	Part 2 Screening Visit ²	Cycle 1						Cycle 2						Cycle 3 & beyond (every 6 weeks)	EOT ¹⁸	Safety Follow-up ¹⁹	PFS ²³²	Overall Survival Follow-Up ²⁰
			D 1	D 8	D 15	D 22	D 29	D 36	D 1	D 8	D 15	D 22	D 29	D 36	D1				
Site Visit	0	1	2	3	4	5	6	7											
Day		-28 to 0	1	8	15	22	29	36	43	50	57	64	71	78	85				

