- 4 All previous cancer treatments, including line of therapy, dates of administration, and best response to treatment on all (both MET-driven and MET-negative) patients will be collected and recorded in the appropriate eCRF at the Part 1 screening visit. During follow-up, cancer treatments administered since discontinuing study treatment will be collected.
- 5 Vital signs include: heart rate, systolic and diastolic blood pressure, height [only at the main study screening] and temperature.
- 6 FFPE tumour sample(s) that meet the specifications in the Laboratory Manual will be analysed prospectively by the sponsor-designated central laboratory by NGS for MET-driven status prospectively, or after study entry in cases where a pre-existing “MET-driven” result is available. See Section 1.4 for qualifying MET-driven alterations.
- 7 If INR and aPTT are normal at baseline, they do not need to be repeated unless clinically indicated during the study. Patients on anti-coagulant therapy should have coagulation testing performed according to standard management guidelines.
- 8 Urinalysis: If 3+ or greater proteinuria is identified by dipstick assessment, a 24-hour urine collection for formal quantification of the level of protein excretion should be performed.
- 9 Women of childbearing potential will have a serum or urine pregnancy test done at main study screening pre-dose Cycle 1 Day 1, on Day 1 of each subsequent cycle, and at treatment discontinuation.
- 10 Triplicate ECGs will be performed during the main study (Part 2) screening period, every week in the first cycle, every cycle thereafter, at the end of treatment visit if not done within the last 6 weeks, and at other times if clinically indicated. Echocardiogram/MUGAs will be performed during the main study (Part 2) screening period, every 12 weeks (± 2 weeks) relative to the first dose of study medication, at the end of treatment visit if not done within the last 6 weeks, and at other times if clinically indicated.
- 11 A 10-mL blood sample for [REDACTED] will be obtained from the patient pre-dose on 1 Day 1 ([REDACTED]). If for any reason the sample is not drawn prior to dosing it may be collected as soon as possible thereafter. Only one sample will be collected. See Section 5.6.

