be performed. The ePRO device and all unused study medication and study medication bottles should be returned.
- 19 A safety follow-up will be performed 30 (± 7) days after discontinuation of study medication, to follow-up on any SAE/AE's and record any subsequent
cancer therapy. If there are no ongoing SAE/AEs at the time of drug discontinuation, the safety follow-up can be done via telephone contact.
- 20 All subsequent anti-cancer therapies and OS status will be documented at least every 12 weeks until death, loss to follow-up, withdrawal of consent, or end
of study, whichever comes first.
- 21 Blood liver functions (AST, ALT, alkaline phosphatase and total bilirubin) will be monitored weekly x 9 and then at the start of each cycle. In some
situations, blood for LFTs may be drawn at a local lab on the days when there is no scheduled clinic visit although the results must be faxed to the treating
institution immediately so they can be evaluated in light of the hepatotoxicity algorithm (Section 6.8.1.2 for savolitinib and Section 6.8.2 for sunitinib) and
entered into the database.
- 22 An IVRS/IWRS transaction needs to be done at every dispensing visit at the start of each cycle. Additionally, every dose reduction needs to be recorded in
IVRS/IWRS.
- 23 Please see section 6.3. From the part 1 screening visit until the part 2 screening visit, only SAEs related to study procedures must be reported (AEs do not
require reporting). From the main study screening (Part 2) onwards, all AEs/SAEs must be reported
- 24 Smoking status (Yes (current smoker) /No (not currently smoking)) will be recorded at the time of the main study screening (Part 2) visit.
- 25 Body weight will be assessed every cycle, and more frequently if clinically indicated. The dose of savolitinib will not change for patients who started the
study at < 50 kg (ie, 400 mg), even if their weight increases to ≥ 50 kg during the course of the study.
- 26 20 mL for [REDACTED] at the Part 1 screening visit only (see Section 5.7.4)
- 27 Only necessary if there are ongoing toxicities
- 28 A tumour biopsy after treatment discontinuation should be strongly encouraged regardless of treatment arm, particularly for patients who had responded to
treatment. See section 5.7.7.
- 29 See Table 2 (Section 5.2.1) for list of chemistry evaluations
- 30 Hepatitis serology includes HBsAg, anti-HBc (qualitative), HBV DNA, HCV antibody, HCV RNA (if HCV antibody is positive)

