7.2.2 Sunitinib

Sunitinib: two 25 mg capsules PO QD, with or without food will be administered in 6-week treatment cycles: 4 weeks on/2 weeks off.

The time of day for administration of sunitinib should be consistent and the actual time the dose is taken should be recorded in the eDiary each day.

If the patient misses a dose of study medication, it should be taken as soon as it is remembered. A missed dose should not be taken, though, if it is close to the next dose. In this case, the next dose should be taken at the regular time. More than 1 dose of sunitinib should not be taken at a time.

If vomiting occurs after taking sunitinib, the patient should be instructed not to retake the dose. Patients should take the next scheduled dose of sunitinib. If vomiting persists, the patient should contact the investigator. Ondansetron or another serotonin-receptor antagonist may be used.

On clinic visit days the patient should be instructed to wait until he/she arrives at the study centre to take their study medication when instructed.

Patients should be advised to bring any unused sunitinib in the original blister packs, in addition to returning any empty blister packs to each clinic visit. Sunitinib dosing compliance

should be reviewed with the patient at each clinic visit, including the visit at the beginning of each cycle when study medication is dispensed.

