- Any AE occurring within the defined 30 day follow up period after discontinuation of investigational product will be included in the AE summaries.
- Deaths will be summarised by primary cause, along with AEs with an outcome of “fatal”.
- Haematology, clinical chemistry, vital signs, ECG, ECHO/MUGA data and concomitant medication will be summarised.
- Any qualitative safety assessments for urinalysis will be presented as is deemed appropriate. This may include, but is not restricted to, presentation of parameters against time, concentration, or shift plots. Appropriate scatter plots will also be considered to investigate trends in parameters compared with baseline.

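### At nominal dates, laboratory and BP checks from Cycle 3, thyroid/LDH tests after Cycle 1 starts, and every on-treatment ECHO/MUGA follow 14 dose-free days on sunitinib and none on savolitinib

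*Protocol*

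**What the plan says.** **Dosing.** Sunitinib "will be administered in 6-week treatment cycles: 4 weeks on/2 weeks off" (Protocol 7.2.2). For the other arm, "Treatment with savolitinib will be given continuously" (Synopsis and 1.4).

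**Visits.** After the weekly visits of Cycles 1 and 2, Table 1 has one column, headed "Cycle 3 & beyond (every 6 weeks", with Day 1 as its only visit and a window of 7 days either side. Haematology, chemistry, liver tests, urinalysis, thyroid/LDH, vital signs and triplicate ECG all sit there.

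- Liver tests "will be monitored weekly x 9 and then at the start of each cycle" (footnote 21).
- Thyroid tests and LDH are done at Part 2 screening and then at the start of every cycle (Table 2, footnote 3).
- ECGs are done "every week in the first cycle, every cycle thereafter" (footnote 10).
- ECHO/MUGA is done every 12 weeks, with a 2-week window either side, counted from first dose (footnote 10 and 5.2.3.2).

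**Dose on the visit day.** For sunitinib, "On clinic visit days the patient should be instructed to wait until he/she arrives at the study centre" (7.2.2). Section 7.2.1 has the same rule for savolitinib.

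**Use of the data.** The safety objective is "To evaluate the safety and tolerability of savolitinib in relation to sunitinib" (2.3), and laboratory values, BP, ECG and echocardiograms are among its outcome measures. Section 8.4.2 states: "Haematology, clinical chemistry, vital signs, ECG, ECHO/MUGA data and concomitant medication will be summarised". Dosing phase is not mentioned.

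**The concern.** The assessment calendar and the sunitinib calendar have the same period. Once visits drop to one per cycle, the scheduled measurement always lands at the same point of the sunitinib cycle, the end of the rest period. A sunitinib effect that recovers wholly or partly in two weeks is then seen at its smallest, while the savolitinib arm is measured during continuous dosing.

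The measures affected are ones that the protocol itself lists as sunitinib risks in 6.8.2.1: hypertension (Grade 3 in 50/375, 13%; severe in 32/375, 9%), falls in ejection fraction, proteinuria and thyroid dysfunction. Table 11 also provides for Grade 3 sunitinib toxicity that lasts no more than 7 days once drug is held. Such an event could be over before a check made after 14 days off.

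Continuous adverse-event collection does not fully fill the gap. Under 6.3.6, deterioration in a mandated laboratory, vital-sign or cardiac measure becomes an adverse event only if it is serious or the reason for stopping treatment, because the measured values are to be summarised in the study report. Most non-serious, symptom-free changes therefore rest on the scheduled values.

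**Working it through.** This is calendar arithmetic; no power or sample-size figure enters. "Dose-free" below means days without a dose; the protocol gives no sunitinib half-life, so residual drug is not modelled.

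**Reproducing the plan's calendar.** Day 1 of cycle k = 42(k − 1) + 1. For k = 2 this gives Day 43 and for k = 3 Day 85, as in Table 1.

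**Position in the sunitinib cycle.** Cycle day = ((study day − 1) mod 42) + 1. Dosing is on cycle days 1–28 and rest on 29–42, so drug is taken on 28/42 = 67% of days. A Day 1 check made before the visit-day dose follows 42 − 28 = 14 dose-free days. ECHO/MUGA at week w falls on study day 7w + 1, and 12 weeks = 84 days = exactly two cycles.

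| Scheduled check | Nominal study days | Dose-free days, sunitinib | Dose-free days, savolitinib |
|---|---|---|---|
| Laboratory and BP, Cycle 3 on | 85, 127, 169, 211 … | 14 | 0 |
| Thyroid/LDH, Cycle 2 on | 43, 85, 127 … | 14 | 0 |
| ECHO/MUGA, weeks 12, 24, 36, 48 … | 85, 169, 253, 337 … | 14 | 0 |

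**Effect of the windows.**
- A Day 85 visit held 7 days early (Day 78) follows 7 dose-free days.
- Held 7 days late (Day 92), it follows 21 dose-free days if the new cycle waits for dispensing. If the patient restarted on Day 85 from remaining stock, it falls 7 days into dosing.
- The week-12 ECHO window runs from Day 71 to Day 99, 29 days. Fifteen carry no prior dose in that cycle phase (rest Days 71–84, plus Day 85 before dosing) and 14 (Days 86–99) are on drug.

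**What is measured on drug.** Nine weekly liver tests counted from Day 1 fall on Days 1, 8, 15, 22, 29, 36, 43, 50 and 57. Days 8, 15, 22, 50 and 57 are in the dosing phase, and Day 29 is the day after the 28th dose. Vital signs are weekly through Cycle 2. ECGs are weekly only in Cycle 1.

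**How many patients reach the affected visits.** Section 8.1 assumes a 4-month exponential median PFS on sunitinib. Day 85 is 84/30.44 = 2.76 months after the start, so 2^(−2.76/4) = 62% would be progression-free. If treatment continues to progression and about 50 patients split evenly, that is about 0.62 × 25 ≈ 15 sunitinib patients.

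**Size of the understatement.** The protocol gives no recovery time. Assuming exponential recovery with half-time h days, the share of an on-drug effect still visible after 14 days is 2^(−14/h):

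| h (assumed) | 3 | 7 | 14 | 28 |
|---|---|---|---|---|
| Share visible | 4% | 25% | 50% | 71% |

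**The case against.** The strongest reply is that the off-drug timing is nominal and the safety data are only descriptive. Visit windows, end-of-treatment assessments (which include laboratory tests, vital signs and, if none in the last 6 weeks, ECG and ECHO/MUGA) and clinically indicated checks can all fall on drug. The Synopsis and 8.4.2 rule out formal testing of safety. Table layout usually belongs to the SAP, which may already deal with dosing phase. All of this stands, and it limits the point to nominal dates and to interpretation. It does not remove it: the protocol fixes the schedule and states a comparative safety objective, and readers compare descriptive columns.

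Three stronger readings are tempting but not supported.

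- **That no value from Cycle 3 on is taken on drug.** This is true only at nominal dates; 14 of the 29 ECHO window days are on drug.
- **That sunitinib toxicity as a whole is under-measured.** Adverse events are collected continuously, patient-reported outcomes run on their own 2- and 4-weekly calendar, and Cycles 1–2 give on-drug laboratory and BP values. Early worst-grade toxicity is therefore captured.
- **That the ECG comparison is tilted against savolitinib.** Savolitinib is also held until the clinic visit. With its half-life of 3.6 to 6.8 hours (1.1.3.1), 2^(−24/3.6) = 1% to 2^(−24/6.8) = 9% of drug remains 24 hours after a dose. The QT effects reported in 1.3 were at 4 and 5 hours. Visit-day savolitinib ECGs may thus be at trough, and no direction can be claimed.

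**Conclusion.** The point holds in a limited form. At nominal dates the later scheduled laboratory and BP values, the thyroid/LDH values from Cycle 2 and all 12-weekly ECHO/MUGA values come at the end of the sunitinib rest period and during continuous savolitinib dosing. For late or cumulative effects that reverse off drug, the scheduled data can understate sunitinib toxicity relative to savolitinib. The exposure is greatest for thyroid function and LVEF, which have no nominal on-treatment measurement in the sunitinib dosing phase even in Cycles 1–2.

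This rests on visits near their nominal day, checks made before the visit-day dose, and effects that recover at least partly within two weeks. The size cannot be derived from the protocol; the 4% to 71% range only illustrates how much depends on recovery speed. It is an avoidable weakness in how a comparative safety objective is served, and it does not invalidate the safety data.

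**What to change.** **Analysis (8.4.2, carried into the SAP before database lock).** Present laboratory, BP, thyroid and ECHO/MUGA summaries by arm, with each sunitinib value classified as on drug or rest period. Derive the class from recorded dosing and assessment dates, which 7.5 already requires in the eCRF and eDiary, so that windows, delays and interruptions are handled as they occurred. State in advance how boundary days are classed (Day 1 before the dose, Day 29). Keep all values in the overall summaries, and draw no between-arm conclusion from values taken in the sunitinib rest period.

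Restricting the comparison to on-drug values is not advised. Sunitinib as a regimen is on drug 67% of the time, so that would risk the opposite bias and discard the later data.

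**Schedule.** The sponsor should reconcile the assessment timing in Table 1, footnotes 10 and 21, and 5.2.3.2 with the sunitinib cycle in 7.2.2. No particular monitoring schedule is proposed here.

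**Cost.** The analysis change means slightly more table work and small numbers per phase with about 50 patients. Any change to the schedule itself would need a new protocol version and ethics approval under 10.5.

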4.1 Screening/enrolment period

Patients will be required to sign a written Part 1 screening ICF for prospective analysis of the MET-driven status using a tumour sample by SAVOIR Clinical Trial NGS assay performed in sponsor designated central laboratory. If this tumour analysis, or a pre-existing MET-driven commercial NGS assay result from the same laboratory, shows that the tumour is MET-driven, patients will be asked to provide informed consent for the main study (Part 2 ICF) prior to starting any additional screening procedures. At the Part 1 screening visit, each potential patient is assigned a unique enrolment code. If a patient withdraws from the study, then the enrolment code cannot be reused.

A pre-existing MET-driven result from a commercial assay from the sponsor designated central laboratory can be used to trigger patient informed consent and entry into the main study, if available. However, a tumour sample from all patients is required for central confirmation of MET-driven tumour status using the SAVOIR Clinical Trial NGS assay.

Demographic data and other characteristics will be recorded and will include: age, gender, race and ethnicity according to local regulations.

A complete medical, surgical and prior anticancer therapy history will be obtained during screening. The medical history is to include smoking history in pack-years. The prior anticancer therapy history is to include all previous treatments (eg, targeted therapy, immunotherapy, cytotoxic chemotherapy, non-TKI anti-angiogenic therapy or combination therapies), line of therapy for each drug or combination, start and stop dates of administration, best response to treatment and reason for discontinuing each drug.

Each patient will undergo the appropriate screening studies as per the study plan (Table 1), either during the Part 1 screening period or to confirm eligibility for the main study during the Part 2 screening within 28 days of signing the ICF for Part 2 (see Sections 3.1 and 3.2). Tumour assessments and other clinical data obtained as standard of care prior to consent may be used for the study provided the assessments fall within the protocol specified period prior to the date of randomisation.

4.2 Treatment period

Evaluations during the treatment period will be performed as detailed in the Study Plan (Table 1).

4.3 Post study-drug follow up

4.3.1 End of Treatment (EOT)

An EOT visit will be conducted as soon as possible and preferably within 7 days following the decision to discontinue study medication.

The purpose of this visit is to:

- (a) discuss any further treatment options and/or follow-up.
- (b) discuss the possibility of a biopsy, which should be strongly encouraged, particularly for patients who had responded to treatment (patients may have signed a consent line for this on the Main Study ICF).
- (c) obtain the required EOT tests (Table 1) and collect the ePRO device after the last set of questionnaires are completed.
- (d) collect any unused study medication and study medication containers from the patient.

Standard laboratory tests, physical exam, vital signs and Karnofsky Performance Status do not need to be repeated if done within the last two weeks. An ECHO/MUGA and triplicate ECGs need to be performed if not done within the last 6 weeks. Blood for [REDACTED] and a pregnancy test need to be performed at the EOT visit. The ePRO device as well as any remaining study medication and study medication containers should be returned.

